#### 4.2.3.3.2 Exploratory Efficacy Endpoints

Exploratory efficacy endpoints include PFS, defined as the time from allocation to the first documented disease progression according to Response Evaluation Criteria in AML or DLBCL (see Section 7.1.2.7.1 and 7.1.2.7.2), or death due to any cause, whichever occurs first, and OS.

#### 4.2.3.4 Planned Exploratory Biomarker Research

##### Planned Genetic Analysis

Understanding genetic determinants of drug response is an important endeavor during medical research. This research will evaluate whether genetic variation within a clinical trial population correlates with response to the treatment(s) under evaluation. If genetic variation is found to predict efficacy or adverse events, the data might inform optimal use of therapies in the patient population. This research contributes to understanding genetic determinants of efficacy and safety associated with the treatments in this study.

#### 4.2.3.5 Future Biomedical Research

The Sponsor will conduct Future Biomedical Research on specimens collected for future biomedical research during this clinical trial. This research may include genetic analyses (DNA), gene expression profiling (RNA), proteomics, metabolomics (serum, plasma) and/or the measurement of other analytes.

Such research is for biomarker testing to address emergent questions not described elsewhere in the protocol (as part of the main trial) and will only be conducted on specimens from appropriately consented subjects. The objective of collecting specimens for Future Biomedical Research is to explore and identify biomarkers that inform the scientific understanding of diseases and/or their therapeutic treatments. The overarching goal is to use such information to develop safer, more effective drugs/vaccines, and/or to ensure that subjects receive the correct dose of the correct drug/vaccine at the correct time. The details of this Future Biomedical Research sub-trial are presented in Section 12.2 - Collection and Management of Specimens for Future Biomedical Research. Additional informational material for institutional review boards/ethics committees (IRBs/ERCs) and investigational site staff is provided in Section 12.3.

### 4.3 Benefit/Risk

Subjects in clinical trials generally cannot expect to receive direct benefit from treatment/vaccination during participation, as clinical trials are designed to provide information about the safety and effectiveness of an investigational medicine.

Additional details regarding specific benefits and risks for subjects participating in this clinical trial may be found in the accompanying Investigators Brochure (IB) and Informed Consent documents.

## 5.0 METHODOLOGY

### 5.1 Entry Criteria

#### 5.1.1 Diagnosis/Condition for Entry into the Trial

Male and female subjects with either AML (de Novo and post-MDS) or DLBCL  $\geq 18$  years of age will be enrolled in this trial.

#### 5.1.2 Subject Inclusion Criteria

In order to be eligible for participation in this trial, the subject must:

1. Be willing and able to provide written informed consent for the trial. Study entry is defined as the date that subject provides written informed consent. The subject may also provide consent for Future Biomedical Research. However, the subject may participate in the main trial without participating in Future Biomedical research.
2. Be  $\geq 18$  years of age on the day of providing written informed consent.
3. Have an ECOG performance status score of  $\leq 1$ .
4. Have an interval of  $\geq 3$  weeks since chemotherapy ( $\geq 6$  weeks for nitrosoureas or mitomycin C), immunotherapy, hormone therapy or any other anticancer therapy (including investigational) or surgical intervention resection, or  $\geq 3$  half-lives for monoclonal antibodies, or  $\geq 5$  half-lives for other non-cytotoxic agents (whichever is longer).
5. Female subjects of childbearing potential must have a negative urine or serum pregnancy test within 72 hours prior to receiving the first dose of study medication. If the urine test is positive or cannot be confirmed as negative, a serum pregnancy test will be required.
6. Female subjects of childbearing potential should be willing to use an adequate method of contraception as outlined in section 5.7.3 - Contraception, for the course of the study through 90 days after the last dose of study medication. Note: Abstinence is acceptable if this is the usual lifestyle and preferred contraception for the subject.
7. Male subjects of childbearing potential 5.7.3 – Contraception, starting with the first dose of trial treatment through 90 days after the last dose of study medication. Note: Abstinence is acceptable if this is the usual lifestyle and preferred contraception for the subject
8. Demonstrate adequate organ function as defined in [Table 1](#) below. All screening labs should be performed within 7 days of treatment initiation.

Table 1 Adequate Organ Function Laboratory Values

System	Laboratory Value
Hematological	
Absolute neutrophil count (ANC)	AML Subjects = No Limit DLBCL Subjects = $\geq 1.0 \times 10^9/L$
Platelets	AML Subjects = No Limit DLBCL Subjects = $\geq 150 \times 10^9/L$ (4 weeks without transfusion)
Hemoglobin	AML Subjects = No Limit DLBCL Subjects = $\geq 8.0 \text{ g/dL}$ (4 weeks without transfusion)
Renal	
Creatinine clearance	$\geq 30 \text{ mL/min}$ calculated according to the Cockcroft and Gault formula or MDRD formula for subjects aged $\geq 65$ years (see Section 12.7)
Hepatic	
Serum total bilirubin	$\leq 1.25 \times \text{ULN}$ OR In case of liver involvement, $\leq 2 \times \text{ULN}$ will be allowed
AST (SGOT) and ALT (SGPT)	$\leq 3 \times \text{ULN}$
Alkaline Phosphatase	If $> 2.5 \times \text{ULN}$ , then liver fraction should be $\leq 2.5 \times \text{ULN}$
Chemistry	
Serum albumin	$\geq 2.8 \text{ g/dL}$
Coagulation	
International Normalized Ratio (INR) or Prothrombin Time (PT)	$\leq 1.5 \times \text{ULN}$
Activated Partial Thromboplastin Time (aPTT)	$\leq 1.5 \times \text{ULN}$

9. Have a histologically or cytologically proven malignancy (AML or DLBCL) according to the WHO 2008 classifications [43][44]. AML includes AML de novo and AML secondary to a pre-existing myelodysplastic syndrome.

The subject must also display the following specific malignancy criteria:

a) AML (de Novo and post-MDS):

- Subjects must have measurable and evaluable disease per tumor response criteria (see Section 7.1.2.7.1).
- Subjects must have  $\geq 5\%$  bone marrow blasts at study entry, without alternative causality (e.g. bone marrow regeneration).
- Subjects  $< 60$  years old in second or further relapse or relapsing after allogeneic stem cell transplantation regardless of number of relapses.

- Subjects  $\geq$  60 years old in first relapse\* with a disease-free interval (DFI)  $<$  12 months, or further relapse. If locally approved therapies exclude patients in this age group, with no prior lines of therapy, these patients will be considered eligible per local requirements.

\*Note: First relapse is also applicable to AML post-MDS patients who have received prior treatment for MDS, but have not received prior treatment for AML.

- Irrespective of age, in subjects relapsing after allogeneic stem cell transplant, the time elapsed since allogeneic stem cell transplant should be  $>$  90 days.
- Subjects with Philadelphia chromosome positive (Ph+) must have received at least two lines of therapy, including 2 bcr-abl tyrosine-kinase (TK) inhibitors (among imatinib, nilotinib and dasatinib), or only one line including one TK inhibitor if the relapse/refractoriness is associated with the detection of a resistance mutation to these inhibitors.

b) DLBCL:

- Subjects must have measurable and evaluable disease per tumor response criteria (see Section 7.1.2.7.2).
- Subjects must have at least one non-irradiated tumor mass  $\geq$  15 mm (long axis of lymph node) or  $\geq$  10 mm (short axis of lymph node or extranodal lesions) on a spiral CT-scan.
- Subjects having failed 2 standard lines of therapy (at least one containing an anti-CD20 monoclonal antibody), or for whom such treatment is contraindicated.

### 5.1.3 Subject Exclusion Criteria

The subject must be excluded from participating in the trial if the subject:

1. Has participated in another clinical trial or treatment with any investigational drug (excluding anticancer treatments) within 30 days prior to study entry.
2. Has other concomitant anticancer treatment.
3. Has persistent grade  $>1$  clinically significant toxicities related to prior antineoplastic therapies (except for alopecia); stable sensory neuropathy  $\leq$  grade 2 NCI-CTCAE v. 4.0 is accepted.
4. Has a known additional malignancy that is progressing or requires active treatment. Exceptions include basal cell carcinoma of the skin, squamous cell carcinoma of the skin, or in situ cervical cancer that has undergone potentially curative therapy.
5. Has taken a similar class of therapy previously (BET inhibitor).
6. Has inability to swallow oral medications or presence of a gastrointestinal disorder (e.g. malabsorption) deemed to jeopardize intestinal absorption of MK-8628.

7. Has known primary CNS malignancy or symptomatic or untreated CNS metastases.
8. Has other serious illness or medical condition, such as active infection, unresolved bowel obstruction, psychiatric disorders, or cerebrovascular accident (within 1 year of study entry).
9. Has known history of Human Immunodeficiency Virus (HIV) (HIV 1/2 antibodies). HIV 1/2 antibodies testing is only required when the investigator has reason to suspect the patient has Human Immunodeficiency Virus infection.
10. Has known active Hepatitis B (e.g. HBsAg reactive) or Hepatitis C (e.g. HCV RNA [qualitative] is detected). Hepatitis B surface Antigen reactive testing and HCV RNA [qualitative] testing is only required when the investigator has reason to suspect the patient has Hepatitis B infection or Hepatitis C infection.
11. Has received high dose chemotherapy followed by autologous stem cell transplantation less than 90 days prior to first dose of MK-8628.
12. Has concomitant (and cannot discontinue) therapy with strong CYP3A4 or CYP2A6 interfering drugs, or any other medication / therapy prohibited by the protocol. Please see Section 5.5 .
13. Has peripheral cytopenia (i.e. auto-immune hemolytic anemia or thrombocytopenia).
14. Has acute promyelocytic leukemia or clinically uncontrolled (i.e. with bleeding) disseminated intravascular coagulation (DIC).
15. Has chronic graft versus host disease (GVHD) or on immunosuppressive therapy for the control of GVHD.
16. Has uncontrolled disease-related metabolic disorder (e.g. hypercalcemia).
17. Is pregnant or breast-feeding.
18. Has any of the following cardiac related conditions:
  - a) Congestive heart failure (except if medically controlled)
  - b) Angina pectoris (except if medically controlled)
  - c) Previous history of myocardial infarction (within 1 year of study entry)
  - d) Uncontrolled hypertension (defined as systolic blood pressure (SBP)  $\geq$  140 mm Hg and/or diastolic blood pressure (DBP)  $>$  90 mm Hg and not adequately managed by anti-hypertensive medication)
  - e) Uncontrolled arrhythmias

## 5.2 Trial Treatment(s)

The treatment to be used in this trial is outlined below in

Table 2 Trial Treatment

Drug	Dose/Potency	Dose Frequency	Route of Administration	Regimen/Treatment Period	Use
MK-8628	20 mg	BID	Oral	Continuous / 21 days per cycle	Experimental
MK-8628	30 mg	BID	Oral	Continuous / 21 days per cycle	Experimental

The first dose of trial treatment will be administered at the trial site in the morning of the Cycle 1 Day 1 Visit, and then again in the evening. Subsequent dosing will be performed twice daily either at the trial site on scheduled visit days, or by the subject (i.e., unsupervised at his/her home), at approximately the same times each day.

All supplies indicated in [Table 2](#) above will be provided centrally by the Sponsor or locally by the trial site, subsidiary or designee, depending on local country operational or regulatory requirements.

For any commercially available product that is provided by the trial site, subsidiary or designee every attempt will be made to source these supplies from a single lot/batch number. The trial site is responsible for recording the lot number, manufacturer, and expiry date for any locally purchased product as per local guidelines unless otherwise instructed by the Sponsor.

The investigator shall take responsibility for and shall take all steps to maintain appropriate records and ensure appropriate supply, storage, handling, distribution and usage of trial treatments in accordance with the protocol and any applicable laws and regulations.

### 5.2.1 Dose Selection/Modification

#### 5.2.1.1 Dose Selection (Preparation)

The rationale for selection of doses to be used in this trial is provided in Section 4.0 – Background & Rationale. There are no specific calculations or evaluations required to be performed in order to administer the proper dose to each subject.

#### 5.2.1.2 Dose Escalation

A twice daily (BID) dose escalation will be performed using a 6+8 two-stage design with continuous DLT rate monitoring via a modified toxicity probability index (mTPI) (Ji design), targeting a maximum 25% DLT rate [1].

Two planned dose levels will be evaluated sequentially: 20 mg BID and 30 mg BID (all continuous daily). See [Table 3](#) and [Table 4](#) for the dose escalation scheme.

Table 3 Dose Escalation Scheme

Dose Level (DL)	MK-8628 (mg/dose) BID Regimen (continuous)	Outcome (#DLT/#Subjects)* / Actions to be taken
DL 1	20	At each DL: - Escalate/de-escalate per DLT rate observed using mTPI (Table 4)
DL 2	30	

\* Evaluated during the first 21 days of treatment

Table 4 Modified Toxicity Probability Interval (mTPI) Design

Number of toxicities	Number of subjects treated at current dose								
	6	7	8	9	10	11	12	13	14
0	E	E	E	E	E	E	E	E	E
1	S	E	E	E	E	E	E	E	E
2	S	S	S	S	S	S	S	S	E
3	D	S	S	S	S	S	S	S	S
4	DU	DU	DU	D	S	S	S	S	S
5	DU	DU	DU	DU	DU	D	S	S	S
6	DU	DU	DU	DU	DU	DU	DU	DU	D
7		DU							
8			DU						
9				DU	DU	DU	DU	DU	DU
10					DU	DU	DU	DU	DU
11						DU	DU	DU	DU
12							DU	DU	DU
13								DU	DU
14									DU

E = Escalate to the next higher dose  
S = Stay at the current dose  
D = De-escalate to the next lower dose  
DU = The current dose is unacceptable  
Target toxicity rate = 25%

**E = Escalate; S = Stay; D = De-escalate; DU = Unacceptable**

Note:

- De-escalation at lowest dose level indicates stopping of trial
- Escalation at highest dose level indicates staying at that level

Each cohort (AML and DLBCL) will be evaluated independently in regards to enrollment and dose level escalation/de-escalation.

Subjects may be enrolled continuously (i.e., without waiting for Cycle 1 completion of subjects who have received the first dose) unless a DLT is observed at the particular dose. If 0 out of the first 6 subjects in a given dose level develop a DLT, then the dose can escalate to the next level without further expansion. If 3 patients out of the first 6 patients develop a DLT, the dose will be de-escalated to the next lowest dose level. If  $\geq 4$  out of the first 6 patients develop a DLT, this indicates an unacceptable toxicity. If 1 to 2 out of the first 6 subjects of a given dose level develop a DLT, expand the current dose level according to [Table 4](#) by continuing enrollment as follows. The number of subjects who are enrolled at that dose but are not yet fully evaluable for DLT assessment may not exceed the number of remaining subjects who are at risk of developing a DLT before the dose would be considered unacceptably toxic (denoted as DU in [Table 4](#)). For example, if 2/7 subjects have experienced a DLT at a given dose level, no more than an additional 3 subjects should be enrolled at this dose level until additional DLT data are available. This is because this dose level would be considered unacceptably toxic if all 3 of the additional subjects experience a DLT (i.e., 5/10 subjects with DLT in [Table 4](#)). To find out how many more subjects can be enrolled, one can count steps in diagonal direction (down and to the right) from the cell (7 subjects, 2 toxicities) to the first cell marked DU.

De-escalation (D) or unacceptable (DU) at the lowest dose level (DL1) indicates stopping of the trial. Escalation (E) at the highest dose level (DL2) indicates staying at that level. Note that while 25% has been the target toxicity rate used to generate the guidelines in [Table 4](#), the observed rate of subjects with DLT at the RP2D may be slightly above or below 25%.

Subjects not evaluable for DLT (i.e. receiving less than 85% of the intended cumulative dose in Cycle 1 for any reason other than toxicity; < 18 days of treatment) and who do not experience DLT will be replaced.

Subjects will receive MK-8628 at the DL they were assigned at treatment allocation throughout the study, or at a reduced dose according to toxicity encountered.

A Safety Review Committee will meet on a regular basis to make decisions related to current dose level duration, escalation, de-escalation, and stopping of the trial. Decisions will be based on available safety and toxicity data. The Safety Review Committee will be composed of an independent medical expert in oncology drug development, the principal investigators (or sub-investigator delegated by the PI) from each of the participating sites, the PK investigator, and Sponsor representatives.

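### At DL1 the cap on subjects with unknown DLT status counts to a DU cell although D also stops the trial there, so in six Stay states it allows one pending subject beyond the stopping boundary

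*Combined protocol and SAP*

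**What the plan says.** Section 5.2.1.2 lets a dose level expand beyond six subjects under this condition: "If 1 to 2 out of the first 6 subjects of a given dose level develop a DLT". During expansion, subjects who are enrolled but not yet evaluable for DLT are capped: their number "may not exceed the number of remaining subjects who are at risk of developing a DLT before the dose would be considered unacceptably toxic", which the text ties to the DU code. The counting instruction is to "count steps in diagonal direction (down and to the right) from the cell (7 subjects, 2 toxicities) to the first cell marked DU". In the worked example, with 2 DLTs in 7 subjects, "no more than an additional 3 subjects should be enrolled at this dose level until additional DLT data are available", because three more DLTs would give 5/10, a DU cell.

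Table 4 has a separate code before DU: "D = De-escalate to the next lower dose". After the example, the same section says: "De-escalation (D) or unacceptable (DU) at the lowest dose level (DL1) indicates stopping of the trial".

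The Safety Review Committee decides on escalation, de-escalation and stopping (end of Section 5.2.1.2). No tighter limit on pending subjects is given, and no rule for subjects still pending when a D cell is reached.

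**The concern.** The cap limits how many subjects are exposed while the outcome of others is unknown. At DL1 two codes have the same consequence, stopping, but the cap looks for only one of them. Where D lies before DU on the diagonal, a subject admitted within the cap can still be in the DLT window when Table 4 already says stop. This happens in states where DLTs are accumulating.

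The decision itself is also left open. One DLT-free result turns 4/9 (D) into 4/10 (S), or 5/11 (D) into 5/12 (S). With one subject pending, acting at once stops the trial at DL1. Waiting for that subject may mean staying at the dose. The section does not say which is intended.

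**Working it through.** **Inputs.** Table 4, rows for 4 and 5 DLTs, columns n = 6 to 14: "4 DU DU DU D S S S S S" and "5 DU DU DU DU DU D S S S". Row 6 is DU up to n = 13 and D at n = 14. The maximum per dose level is 14 (Section 8.9).

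**Plan's own figure.** From 2/7 the diagonal is 3/8 = S, 4/9 = D, 5/10 = DU. The first DU cell is three steps away, so the stated cap of 3 reproduces. The first D cell is two steps away.

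**Are the D cells genuine?** I rebuilt the table with the mTPI rule, using the 25% target of Table 4 and the Beta(1,1) prior that Section 8.6.1 states for the DLT interval. The documents do not give the interval half-width or the DU cut-off, so I assumed 0.05 and 0.95. All 63 cells for 0 to 6 DLTs agree, and half-widths of 0.02, 0.03 and 0.04 give the same result. P(rate > 25%) is 0.922 at 4/9 and 0.946 at 5/11, just under the cut-off. It is 0.966 at 5/10 and 0.976 at 6/12. The D cells are not damage from text extraction.

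**All Stay states.** Of the 22 S cells at n = 6 to 13, 12 have a DU cell ahead on the diagonal. In 6 of those D comes first, always by one step. Let p be the true DLT rate, with independent subjects read in turn and the cap full. The chance of reaching D with the extra subject unread is p to the power of the steps to D.

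| State | Steps to DU (cap) | Steps to D | Chance at p = 25% / 40% / 50% |
|---|---|---|---|
| 1/6 | 4 | 3 (4/9) | 1.6% / 6.4% / 12.5% |
| 2/7 | 3 | 2 (4/9) | 6% / 16% / 25% |
| 3/8 | 2 | 1 (4/9) | 25% / 40% / 50% |
| 2/8 | 4 | 3 (5/11) | 1.6% / 6.4% / 12.5% |
| 3/9 | 3 | 2 (5/11) | 6% / 16% / 25% |
| 4/10 | 2 | 1 (5/11) | 25% / 40% / 50% |

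For example, from 2/7 at 40%: 0.4 × 0.4 = 0.16. The two counts agree at 2/6 (2), 3/7 (1), 2/9 (4), 3/10 (3), 4/11 (2) and 5/12 (1).

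**How often would the cap be full?** Section 1.0 gives at most 56 subjects and about 20 months, so 28 per cohort. With 30-day months and even accrual, 600 / 21 = 28.6 DLT windows and 28 / 28.6 = 0.98 subjects per cohort per window. With Poisson arrivals (assumed), the chance of at least 4, 3 or 2 arrivals in one window is 2%, 8% or 26%. If accrual is twice as fast (mean 1.96), it is 14%, 31% or 58%. Since the 20 months include follow-up, actual accrual would be somewhat faster than 0.98.

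**The case against.** The strongest defence is that the rule means what it says. The cap is tied to DU in the sentence, in the example and in the counting instruction, and Table 4 defines D and DU separately. An enrolment ceiling and a decision rule can both be obeyed. This stands for DL2: there D calls for moving to the lower dose but does not declare the current one unacceptable, so counting to DU is a deliberate and consistent choice. It does not stand for DL1, where the section gives D and DU the same consequence.

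A second defence is that the columns of Table 4 count subjects treated. With three pending at 2/7, ten have been treated, so two DLTs would read as 4/10 = S and D would never appear. However, the example leaves pending subjects out of the 7 and moves one column for each further subject. Under the continuous monitoring that the section describes, 4/9 is therefore a state that can be met. What remains of this defence is the ambiguity over pending outcomes.

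Third, the chances above need a full cap, which planned accrual makes uncommon for caps of three or four, though less so for a cap of two. That limits the size.

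Fourth, Section 1.0 records that enrolment has ended and one subject remains. The point now bears on how past DL1 decisions are read and on any reuse of the wording.

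**Conclusion.** The conflict is firm at DL1 and small: exactly one subject in each of six states, including the protocol's own example and 1/6, one of the two states that start expansion. The chances in the table rest on assumed DLT rates, independence, subjects read in turn and a cap that is full. The lower end applies if the true rate is at the 25% target.

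A reader might infer that the cap lets subjects be dosed past the point where Table 4 closes the dose at any level. The documents do not support that: at DL2 only DU marks the dose as unacceptable, and the cap is explicitly tied to DU. Nor is the example miscounted, since its figure of 3 follows exactly from the stated rule. The inconsistency is between that rule and the DL1 stopping sentence.

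**What to change.** In Section 5.2.1.2, reconcile four items: the cap sentence, its worked example, the D cells of Table 4 and the DL1 stopping sentence. At DL1 the cap and the stopping rule should rest on the same boundary. State separately what applies at DL2. Also state how pending subjects' outcomes count once a D cell is reached, since 4/9 and 5/11 are D while 4/10 and 5/12 are S. Which boundary is clinically right is for the sponsor and the Safety Review Committee.

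The edit is a few sentences. If the cap were aligned to D, the cost would be at most one fewer pending subject in the six states and a brief accrual pause. There could also be a somewhat higher chance of stopping at DL1. If all pending subjects are read before deciding, then from 2/7 at a true rate of 25% that batch would stop the trial with chance 0.25² = 6.3%, against 0.25³ = 1.6% under the present cap. If D is acted on as soon as it is reached, the chance of stopping is the same under either cap and only exposure changes.
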